2.2 Randomization

Randomization assignments are at the participant level and are assigned at baseline. Randomization will be stratified by enrolling site and may also be stratified by severity of illness and/or other arm-specific criteria. In general, allocation will be equally distributed across arms for which the participant is eligible, but may be altered with future arm-specific appendices. If a participant is eligible for multiple arms, they would be equally randomized (1:1) to all eligible arms.

ACTIV-4a: Possible Example Scenarios in Master Protocol

3 Objectives and Purpose

The overarching objective of this adaptive platform design is to iteratively learn which treatment strategies, including but not limited to antithrombotic strategies, are best for reducing the primary, secondary, and safety outcomes. Additional alternative strategy(-ies) will be compared to the current standard of care arm, which may trigger new standard of care designated arms as appropriate based on interim analysis results and evolving literature. This process will continue until no new strategies replace the standard of care or potential options for additional interventions are exhausted.

4 Study Design and Endpoints

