8.3 Model Priors

The treatment effects for arm a , within disease subtype s are modeled with the θ_s parameters. The β parameters model any covariate effects included in the model. The λ parameters model the effect of time within the pandemic.

The ordinal endpoint rates are modeled using an inverse Dirichlet model where the individual probabilities for the 23 outcomes are based on 1 patient's weight on equally likely outcomes.

$$\text{logit}(\alpha_{y,s}) \sim \text{Dirichlet}(1 * P), \text{where } P \propto 1$$

The site effects, $v_{Site,s}$, are modeled using a hierarchical model where site is nested within the country of the site:

$$v_{Site,s} \sim N(\mu_{country,s}, \tau_{country,s}^2), \text{site} = 2, \dots, N_{Site}$$

$$\mu_{country,s} \sim N(0,1); \tau_{country,s}^2 \sim IG(0.25,0.1), s = 1,2$$

A referent site, expected to be the largest enrolling site, will be set such that $v_{Site} \equiv 0$. The hyper-parameters of the site hierarchical model are separate by disease state s .

The effect of time (T) is modeled using a second-order normal dynamic linear model separately by disease state, s . The most recent two time periods are modeled as the referent time epochs with the time parameters set to 0. The preceding time epochs are modeled as a normal dynamic linear model as:

$$\lambda_1 = \lambda_2 \equiv 0$$

$$\lambda_3 \sim N(0,0.15^2)$$

$$\lambda_T - 2\lambda_{T-1} + \lambda_{T-2} \sim N(0, \tau_{Time}^2), T \geq 4$$

The treatment effect parameters are set against a control arm, which will be labeled in the arm-specific appendix. The treatment effect for the control arm, labeled as arm $a = 1$, will be set to 0 for each of the disease states:

$$\theta_{1,s} \equiv 0.$$

The effect of each treatment arm introduced will typically be modeled hierarchically across disease subtypes. The modeling of the treatment arms will be specified in appendices.

Any additional covariates included in the model will have independent $N(0,1)$ priors unless otherwise specified.

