9.1.2 Randomization

Randomization assignments are performed for participants at baseline. Randomization will be equal across all arms a patient is eligible. Randomization stratification will be done by site, and disease subtype (ICU and non-ICU level care) and/or other arm-specific criteria.

10 Source Documents and Access to Source Data/Documents

The ACTIV-4 Platform will have uniform policies describing what source documents are, how to make corrections, and who can access them.

11 Quality Assurance and Quality Control

The ACTIV-4 Platform will have uniform policies for quality assurance at the data entry level and site monitoring.

12 Ethics/Protection of Human Subjects

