A9.9 Safety Analyses

The rate of infusion-related SAEs will be monitored. The rates of ISTE major bleeding, ICH and fatal bleeds, major thrombotic events, and mortality will be monitored in comparison to the standard of care arm as well as to any additional arms added to the platform trial. The DSMB will review the number of events, the event rates, and the posterior mean and 95% credible intervals for the event rates, difference between arms, and odds-ratios between arms will be summarized.

A9.10 Statistical Analyses

This arm will be compared to the Crizanlizumab standard of care arm. Patients eligible for Crizanlizumab will be randomized to either Crizanlizumab or no Crizanlizumab. These same patients may be randomized to other therapies within this master protocol. The comparison will be between those randomized to Crizanlizumab vs those randomized to no Crizanlizumab.

The primary Bayesian statistical model (see Statistical Analysis Plan) will be used for modeling the effect of Crizanlizumab in comparison to no Crizanlizumab with the following exceptions:

1. The model will contain a main effect for each other therapy that was randomized for each patient.
2. Site will not be included in the primary analysis model, but instead the country for the site will be included.

The Statistical Analysis Plan presents the interim analysis schedule and adaptive decision rules.

The primary analysis for Crizanlizumab will be restricted to only patients in the intent-to-treat for Crizanlizumab. This group are those patients that have been randomized to potentially receive Crizanlizumab. No patients that were not randomized to yes/no for Crizanlizumab will be used in the primary analysis for Crizanlizumab.

A9.11 Safety Reporting

The following safety information should be reported:

- Serious Adverse Events (SAEs), excluding study endpoints, in patients exposed to crizanlizumab should be reported within 14 calendar days of becoming aware of it, including those which may have been the reason for the patient to discontinue infusion.
- Any other relevant safety information listed below in patients exposed to crizanlizumab should be reported within 14 calendar days of becoming aware of it:
 - overdose (with or without clinical symptoms),
 - intentional drug misuse/abuse (with or without clinical symptoms),
 - medication errors (including maladministration, dispensing or prescribing errors, with or without clinical symptoms),

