### 12.1. Primary Analysis of Primary Endpoint

The **primary analysis model** is a Bayesian cumulative logistic model for the ordinal primary endpoint. The model is described below.

The primary endpoint has 23 possible ordered outcome values. Let the outcome for a patient labeled as  $Y_i$ , with possible values,  $-1$  (death),  $0, 1, \dots, 21$ . A cumulative logistic model is specified. The model is structured so that an  $OR > 1$  implies clinical benefit. The model has factors for:

1. Each level of the ordinal endpoint
2. Each global site, nested within country
3. Age;  $\le 39, 40-49, 50-59, 60-69, 70-79, 80+$
4. Sex

5. Time: 2-week epoch bins of time working backwards from the last enrolled patient.
6. Hx cardiovascular disease, including HTN, and/or diabetes
7. Severe/Moderate cohort
8. For severe (type of organ support, invasive mechanical ventilation vs. not)
9. For moderate (the amount of O2 required, no O2, > 0 but <= 2, >2)
10. An effect for each intervention; the effects for P2Y12 are nested across cohorts
11. All sites within a country that have <5 patients randomized will be combined into a single site within that country.
12. For the primary outcome, if there is an outcome in the ordinal scale that did not occur in the data, then that outcome will be combined the next worse outcome. This is done for model stability. For example, if the outcome 11 never occurred, then a combined outcome of 10 & 11 will be modeled for the analysis.
13. If analyzing a single cohort that does not allow for the hierarchical structure in the model, the hierarchical structure of the treatment parameters will be replaced by a standard normal prior unless otherwise specified.

The primary analysis model will be referenced with certain model assumptions for sensitivity analyses. For example, the “time effects” in the model could be assumed to be 0.

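### Arms E and F replace site with country in the primary model although randomization is stratified by site: a permitted but unexplained choice that modestly lowers the chance of declaring superiority

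*Protocol*

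**What the plan says.** On randomization, Protocol 2.2 states: "Randomization will be stratified by enrolling site and may also be stratified by severity of illness and/or other arm-specific criteria". Protocol 9.1.2 agrees: "Randomization stratification will be done by site, and disease subtype (ICU and non-ICU level care) and/or other arm-specific criteria". Neither Appendix 9 nor Appendix 10 changes this.

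On analysis, Protocol 8.3 says that the site effects "are modeled using a hierarchical model where site is nested within the country of the site", with separate hyper-parameters for each disease state. The SAP for the P2Y12 comparison also keeps site nested in country (12.1, item 2) and adds a rule for sparse sites (item 11): "All sites within a country that have <5 patients randomized will be combined into a single site within that country".

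For Arm E, A9.10 takes the primary model with two exceptions. The second is: "Site will not be included in the primary analysis model, but instead the country for the site will be included". A10.11 uses the same words for Arm F. No reason is given in either place, and no analysis with site is named. Protocol 8.2 describes its model as generic and allows arm-specific appendices to depart from it.

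**The concern.** An analysis should normally reflect the factors used to restrict randomization. Stratifying by site balances the arms within site and so removes between-site variation from the treatment comparison. A model without site does not know this and states more uncertainty than the design leaves.

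The documents give reason to expect site to be prognostic here. Standard of care is set locally (Protocol Appendix 1), outcomes are assessed locally (Appendix 2), and SAP 4.3 acknowledges that the provision of organ support varied. The endpoint counts days on support, which depends partly on hospital practice. Country cannot capture differences between hospitals in the same country.

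At stake is the chance that an effective agent reaches a superiority conclusion, and the meaning of the reported odds ratio beside that of the P2Y12 comparison, which is conditional on site.

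**Working it through.** **Inputs from the documents.** Stratification by site; 1:1 allocation ("they would be equally randomized (1:1) to all eligible arms", Protocol 2.2); a 23-level ordinal endpoint with a proportional-odds model (SAP 4.3); a superiority trigger of 0.99 posterior probability that the odds ratio exceeds 1, stated for P2Y12 only (SAP 4.4).

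**Inputs that are missing and therefore assumed.** The appendices give no sample size, trigger or site variance for Arms E and F, so there is no stated figure to reproduce. For the within-country site variance Protocol 8.3 offers only a prior, "IG(0.25,0.1), s = 1,2", which is diffuse and is not evidence about the actual spread. The site SD, σ, on the log-odds scale is therefore varied.

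**Step 1: shift in the odds ratio.** The logistic-normal approximation gives

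log OR without site = log OR with site ÷ √(1 + 0.346σ²).

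The divisor is √1.031 at σ = 0.3, √1.0865 at 0.5, √1.221 at 0.8 and √1.346 at 1.0, so log OR is multiplied by 0.985, 0.959, 0.905 and 0.862. A site-conditional odds ratio of 1.50 becomes about 1.49 (σ = 0.3), 1.48 (0.5) and 1.42 (1.0). An odds ratio of 1.30 becomes 1.295 (0.3), 1.286 (0.5) and 1.268 (0.8).

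**Step 2: a ceiling on the efficiency loss.** Squaring the factors gives 0.970, 0.920 and 0.819 at σ = 0.3, 0.5 and 0.8, that is, losses of 3%, 8% and 18% of effective sample size. These are upper bounds, because they treat every site effect as perfectly known.

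**Step 3: simulation.** Assumptions: 800 patients per cohort; permuted blocks of 4 within site; 5 or 20 patients per site; 800 replicates per setting. The severe outcome has 30% deaths, 15% with zero days and the rest spread evenly. The moderate outcome has 8% deaths, 75% at 21 days and the rest spread. Each data set was fitted without site and with a shrunken site effect. The trigger was a normal-approximation posterior probability above 0.99 at a single look. Results for a true odds ratio of 1.5:

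| σ | Mean OR, without → with site | Trigger, severe | Trigger, moderate |
|---|---|---|---|
| 0.3 | 1.49–1.50 → 1.50–1.51 | change of at most about 1 point | change of at most about 1 point |
| 0.5 | 1.47–1.49 → 1.49–1.50 | 81–82% → 83% | 49–52% → 51–52% |
| 1.0 | 1.41 → 1.46–1.49 | 68% → 79–80% | 42% → 47–49% |

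At a true odds ratio of 1.2 the largest change at σ = 0.5 was 2.5 points (severe, 20 per site, 16.0% → 18.5%). At σ = 1.0 the same setting moved from 9.6% to 16.8%. The P2Y12 futility trigger at odds ratio 1.2 moved by about 1 point or less.

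**Step 4: where the loss arises.** The reported standard error does not grow when site is left out. For the severe cohort at odds ratio 1.5 it is 0.1246 without site and 0.1246–0.1248 with site at σ = 0.3–0.5, and 0.1248 against 0.1263–0.1264 at σ = 1.0. What changes is its relation to the true sampling SD under stratified randomization. With no effect and 20 patients per site (severe), the model without site reports 0.1247 against a true 0.1190 at σ = 0.5, and 0.1251 against 0.1062 at σ = 1.0. The ratios are 1.05 and 1.18. With site the ratios are 0.1247/0.1237 = 1.01 and 0.1269/0.1219 = 1.04.

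**Step 5: no effect.** At σ = 1.0 and true odds ratio 1, superiority was declared in 0.2–0.9% of replicates without site and 0.9–1.1% with it. The omission is conservative.

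**Limits.** Monte Carlo error on each trigger probability is about 1.3–1.8 points, less on paired differences. The site fit used the true σ, which slightly favours including site.

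**The case against.** The strongest reply is that nothing here is an error. Protocol 8.2 permits the departure, both appendices declare it openly, and country stays in the model, so only within-country variation is lost. That stands.

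Second, Protocol 8.1 promises each arm its own SAP, and the only SAP available covers the antiplatelet comparison. A plan for Arms E and F may explain the choice or add an analysis with site. That also stands and cannot be checked here. The 0.99 trigger is likewise borrowed from P2Y12.

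Third, with about 400 sites planned across the platform and site effects estimated separately by disease state, many sites may be too small to support a stable fit, and pooling very small sites moves the model toward country-only adjustment. This limits the likely gain but does not require dropping site. Shrinkage and the pooling rule exist for sparse sites, and SAP 12.6 allows documented changes if a model is unstable.

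A reader might infer that omitting site biases the treatment effect. It does not: the shift toward 1 is non-collapsibility, the country-adjusted odds ratio is a valid but more marginal quantity, and the null is preserved. A reader might also infer that the reported interval becomes wider or that 8% or 18% of the sample is thrown away. Step 4 contradicts the first, and the percentages are only ceilings under assumed site SDs.

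**Conclusion.** The point holds as a modest, correctable inefficiency. The Arm E and F primary models ignore a factor used to randomize, and the appendices do not say why. The consequences are a posterior somewhat too wide for the stratified design, an odds ratio slightly nearer 1, and a lower chance of declaring superiority. False-positive risk does not rise.

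At a true odds ratio of 1.5 the loss is negligible if the within-country site SD is 0.3, about 0 to 2 points at 0.5, and about 4 to 12 points at 1.0. These figures rest on 800 patients per cohort, the assumed site sizes and outcome distributions, and the P2Y12 trigger at a single look. Because the documents do not give the site SD, it is not established that the loss is material in this trial. The case for change is that restoring a shrunken site effect cost essentially nothing in these simulations when site variation was small and recovered a useful amount when it was large.

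**What to change.** Delete exception 2 in A9.10 and in A10.11. Keep the Protocol 8.3 site effect, hierarchical and nested in country, and carry over the rule in SAP 12.1 item 11 that pools sites with fewer than 5 patients within a country. Prespecify the country-only model as a sensitivity analysis and as the documented fallback if the site model does not converge, in line with SAP 12.6.

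If the sponsor prefers to keep country-only as primary, the minimum is to state the reason and to prespecify the hierarchical site model as a sensitivity analysis.

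The cost is one line in each of two appendices, matching text in the Arm E and F analysis plans, and a longer model run. The platform already has the model. If most sites turn out to be very small, the gain will be slight.

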Appendix 10: Standard of care plus SGLT2 inhibitor

A10.1 Background and Rationale for Arm F

Patients who are hospitalized with coronavirus disease 2019 (Covid-19) remain at high risk for multi-organ failure and death. Given the dearth of efficacious therapies that reduce the risk of major clinical events, there is a large unmet need for additional treatment options.

Sodium–glucose cotransporter 2 (SGLT2) inhibitors provide organ protection and reduce cardiovascular and kidney events in large trials of predominantly ambulatory patients with type 2 diabetes, cardiovascular and/or kidney disease (1-3). Although the mechanisms underlying these benefits remain a subject of investigation, prior studies have shown that SGLT2 inhibitors favorably affect a number of pathways that are dysregulated in the setting of acute illness (including Covid-19) such as inhibition of glycolysis (a pathway that can be used by respiratory pathogens) and stimulation of lipolysis, reduction in oxidative stress and inflammation, as well as improved endothelial function and oxygen carrying capacity, and protection against capillary leak (4-11). These effects may help prevent multi-organ damage and improve recovery in Covid-19.

A previous large trial of SGLT2 inhibitor dapagliflozin in patients with chronic kidney disease demonstrated significant reduction in all-cause death, driven predominantly via lower rates of non-cardiovascular (and specifically infection-related) death (12). Large observational studies have also suggested lower risk of major clinical events in patients hospitalized with Covid-19 that were on background SGLT2 inhibitor therapy (13).

The effectiveness and safety of SGLT2 inhibitor dapagliflozin was investigated in the Dapagliflozin in Respiratory Failure in Patients with Covid-19 (DARE-19) which randomized 1250 patients with cardiometabolic risk factors hospitalized with Covid-19 across 7 countries and 95 sites to either dapagliflozin 10 mg daily or placebo for 30 days (14). Treatment was continued in case of patients' clinical status deterioration requiring ICU level care, and regardless of hospital discharge. Fewer patients treated with dapagliflozin experienced the composite endpoint of respiratory, cardiovascular or kidney failure, or death from any cause at 30 days (HR 0.80, 95% CI 0.58-1.10); although this was not statistically significant, the trial only accrued 156 of the initially planned 380 events (due to a large decline in event rates during the course of the trial) and therefore did not have sufficient power for this endpoint. Importantly, the results were directionally favorable to dapagliflozin across each component of this composite outcome, including death from any cause (HR 0.77, 95% CI 0.52 – 1.16).

Dapagliflozin was well tolerated, with fewer serious adverse events than placebo.

Dapagliflozin is considered as the preferred SGLT2 inhibitor for this arm of the trial, given the following considerations: 1) it is the only agent in the class for which the efficacy and safety data from randomized controlled trials in patients hospitalized with Covid-19 is available 2) it has a well established safety profile across various patient populations and 3) extensive clinical experience and broad availability in more than 90 countries. However, because the potential benefits of SGLT2i are expected to represent a class effect, other SGLT2 inhibitors (such as empagliflozin) can be used if dapagliflozin is not available at the participating hospital site.

Pharmacology: Dapagliflozin is a highly selective SGLT2 inhibitor that is administered at the dose of 10 mg once daily, via enteral route. Dapagliflozin is 78% bioavailable. The median time to reach

maximum concentration is 2 h. The half-life is 12.9 h. The route of elimination is via kidneys and GI tract.

Empagliflozin is a highly selective SGLT2 inhibitor that is administered at the dose of 10 mg once daily, via oral route. The median time to reach maximum concentration is 1.5 h. The half-life is 12.4 h. The route of elimination is via kidneys and GI tract.

Safety: Dapagliflozin has been used extensively in clinical practice (predominantly for management of Type 2 diabetes and heart failure) since its approval (in European Union) in 2011, has been evaluated in tens of thousands of patients in clinical trials across Type 2 diabetes, heart failure and chronic kidney disease, and prescribed to millions of patients (with marketing authorization in more than 90 countries).

The safety of dapagliflozin in patients hospitalized with Covid-19 was specifically evaluated in the DARE-19 Trial, where it was well tolerated. Specifically, fewer patients treated with dapagliflozin as compared with placebo experienced serious adverse events (including fatal SAEs), adverse events leading to discontinuation of study medication, and adverse events of acute kidney injury. Due to potential concerns regarding the risk of diabetic ketoacidosis in patients treated with dapagliflozin, a proactive surveillance program was used in the DARE-19 trial, with mandatory daily monitoring of acid-base status among those with Type 2 diabetes (15). Only 2 cases of DKA were observed in patients treated with dapagliflozin (versus 0 with placebo). Both of these occurred in patients with Type 2 diabetes, were non-severe, and resolved rapidly after discontinuation of study medication.

A10.2. Eligibility Criteria for Arm F

A10.2.1 Inclusion Criteria for Arm F

Inclusion criteria contained in the master protocol in addition to the following:

Moderate illness severity – defined as non-ICU level of care at the time of randomization (not receiving high flow nasal oxygen (HFNO), non-invasive ventilation (NIV), invasive ventilation (IV), vasopressors or inotropes, or extracorporeal membrane oxygenation (ECMO))

OR

Severe illness severity – defined as ICU level of care at the time of randomization (receiving HFNO, NIV, IV, vasopressors or inotropes, or ECMO)

For moderate illness severity, participants are required to meet one or more of the following risk criteria:

1. Age \geq 65 years or
2. ≥ 2 of the following:
 - O₂ supplementation > 2 liters per minute
 - BMI \geq 35
 - GFR \leq 60
 - History of Type 2 diabetes
 - History of heart failure (regardless of ejection fraction)
 - D dimer \geq 2x the site's upper limit of normal (ULN)
 - Troponin \geq 2x the site's ULN
 - BNP \geq 100 pg/mL or NT-proBNP \geq 300 pg/mL
 - CRP \geq 50 mg/L

A10.2.2 Exclusion Criteria for Arm F

In addition to the exclusion criteria noted in the master protocol, arm-specific exclusion criteria are as follows:

- Known hypersensitivity to any SGLT2 inhibitors
- Type 1 diabetes
- History of diabetic ketoacidosis
- eGFR <20 and/or requirement for renal replacement therapy
- Open label treatment with any SGLT2 inhibitor

A10.3 Study Agents

Arm F consists of the combination of standard of care plus an SGLT2 inhibitor (dapagliflozin preferred). Please refer to the manual of operations for recommended standard of care, including standard of care antithrombotic therapy for moderate and severe illness severity, respectively.

A10.3.2. SGLT2 inhibitors

Dapagliflozin (preferred SGLT2 inhibitor for this arm) is a highly selective sodium glucose cotransporter 2 (SGLT2) inhibitor. In patients randomized to receive SGLT2 inhibitors, dapagliflozin (or empagliflozin) will be administered orally at 10 mg once daily. If patient requires intubation and mechanical ventilation, or cannot receive oral medications for another reason, the tablet can be crushed and flushed down the feeding tube.

In the international, multi-center, double-blind, placebo-controlled DARE-19 trial of dapagliflozin for prevention of organ failure or death in patients hospitalized with Covid-19, fewer patients treated with dapagliflozin experienced the composite endpoint of respiratory, cardiovascular or kidney failure, or death from any cause ((HR 0.80, 95% CI 0.58-1.10); although this was not statistically significant due to fewer accrued events than originally anticipated. The results were directionally favorable to dapagliflozin as compared with placebo for each component of this composite outcome (respiratory, cardiovascular, kidney decompensation, and death from any cause). Dapagliflozin was well tolerated, with fewer serious adverse events than placebo.

Dapagliflozin is considered as the preferred SGLT2 inhibitor for this arm of the trial, given the following considerations: 1) it is the only agent in the class for which the efficacy and safety data from randomized controlled trials in patients hospitalized with Covid-19 is available 2) it has a well established safety profile across various patient populations and 3) extensive clinical experience and broad availability in more than 90 countries. However, because the potential benefits of SGLT2i are expected to represent a class effect, other SGLT2 inhibitors (such as empagliflozin) can be used if dapagliflozin is not available at the participating hospital site.

Pharmacology: The main action of SGLT2 inhibitors is enhanced excretion of glucose and sodium via inhibition of sodium glucose cotransporter 2 in the proximal tubule. Dapagliflozin is administered enterally, and is 78% bioavailable. The median time to reach maximum serum concentration (Tmax) is 2 hours. The mean terminal elimination half-life (T1/2) is 12.9 hours. Dapagliflozin is predominantly excreted via kidneys (75%) and GI tract (21%). Empagliflozin is a highly selective SGLT2 inhibitor that is administered at the dose of 10 mg once daily, via enteral route. The median time to reach maximum concentration is 1.5 h. The half-life is 12.4 h. The route of elimination is via kidneys (54%) and GI tract (41%).

There are no meaningful drug-drug interactions reported with dapagliflozin (or empagliflozin), with exception of enhanced glucose-lowering when co-administered with insulin or insulin secretagogues.

Storage: SGLT2 inhibitors will be stored per local pharmacy policies and procedures.

Administration: Dapagliflozin (or empagliflozin) will be administered orally (or via feeding tube, if applicable) at the dose of 10 mg daily. The first dose should be administered as soon as possible after randomization.

A10.3.3 Participants receiving additional Covid-19 therapies

Co-administration or prior administration of other Covid-19 therapies (other than an SGLT2 inhibitor) as part of standard of care or as part of another investigational therapy is permitted.

A10.4 Participants who become pregnant within 90 days of study treatment

Sexually active women of childbearing potential must use highly effective form(s) of birth control (contraception) until the treatment with an SGLT2 inhibitor has been completed. If a participant reports being pregnant during the 28 day treatment period the SGLT2 inhibitor will be permanently discontinued.

A10.5 Duration of treatment

Treatment with dapagliflozin (or empagliflozin/another SGLT2 inhibitor) will be continued through Day 28.

A10.6 Discontinuation of study intervention

At any time, patients are free to discontinue treatment or withdraw from the study, without prejudice to further treatment. A patient that decides to discontinue treatment will always be asked about the reason(s).

Discontinuation from investigational product is not the same as complete withdrawal from the study. It is essential to collect data for all patients throughout the study. For that reason, a patient who discontinues treatment should optimally continue to follow up study assessments up to and including day of discharge (or Day 28). Alternatively, if the patient does not agree to this approach, modified follow-up should be arranged (eg, less frequent assessments, one contact at Day 30, or other means). Patients who agree to some kind of modified follow up are still participating in the study.

If a patient for some reason cannot be reached during the study, every attempt should be made to retrieve as much information regarding this patient as possible. The site should continuously try to reach the patient, the patient's family, or pre-identified contact person and search for information regarding the patient's status in applicable sources to protect the validity of data. These attempts should be documented.

A10.7 Study Schedule

Activity	Screening/ Enrollment	Hospital Duration	28 days or hospital discharge ⁺	90 days post randomization and long term follow-up ⁺⁺
Eligibility				
Consent	X			
Demographic and Medical History	X			
Assessment of Inclusion/Exclusion criteria	X			
Self-reported race/ethnicity and sex	X			
Pregnancy Test, for women of childbearing potential	X			
Study Drug Administration				
Randomization	X			
Study treatment	X	X	X	
Study Procedures				
Height	X			
Weight	X			
Vital signs	X	X		
Concomitant medications	X	X		
WHO ordinal assessment	X	X	X	X
Quality of Life and Functional Status [#]	X			X
Outcomes assessment		X	X	X
SOC Laboratory Assessments				
Chemistry panel	X	X	X [^]	
CBC with platelet count	X	X	X	
Blood Group [*]	X			
PT, PTT if known	X	X		
D-dimer ^{***}	X	X	X	
Troponin ^{****}	X	X	X	
Coagulation and inflammatory markers ^{*****}	X	X	X	
Optional Biorepository	X	X		
BNP or NT-proBNP ^{*****}	X	X	X	

[^]Chemistry panel (e.g. creatinine, acid-base) is strongly recommended to be measured at days 1,3,7,14, and at hospital discharge. Monitoring of acid-base balance in patients with T2DM during hospitalization represents a standard of care in most institutions; if there is a clinical concern for DKA due to acid base status, this should be further investigated (see A10.8.1).

^{*}Blood group taken from hospital record or self-report if that is not available.

^{**} Frequency and mode (Anti-factor Xa/PTT) of testing will be based on site routine. Anti-factor Xa monitoring is preferred over PTT

^{***} Baseline D-dimer is recommended. All values collected should be recorded.

^{****}Strongly recommended as part of routine care, all values collected should be recorded

^{*****}Optional, listed in case report form

[#]Participants may be assessed for functional status and quality of life that reflects baseline status pre-COVID illness and functional status and quality of life at 90 days when contacted to ascertain vital status. (Instruments detailed in the manual of operations).

⁺Assessments indicated in the table above will be ascertained at discharge or 28 days, whichever comes first. Participants must be followed for vital status until discharged from the hospital or another care facility (if transferred on organ support) for up to 90 days. To maximize retention, participants will be contacted intermittently post-discharge, and that contact will be recorded in the EDC. For participants discharged prior to Day 28, this will include information about treatment adherence, to be collected as close to 30 days post-randomization as possible.

⁺⁺Participants will be contacted to ascertain vital status.

A10.8 Potential Risks & Benefits

A10.8.1 Known and Potential Risks

The standard of care plus SGLT2 inhibitor group may receive anticoagulants and/or antiplatelet or additional antithrombotic therapies agents as part of standard care. SGLT2 inhibitors are not known to have any impact on bleeding or thrombosis.

The safety profiles of dapagliflozin (and empagliflozin) are already well established from prior clinical studies in various clinical settings. These studies have demonstrated that SGLT2 inhibitors are generally safe and well tolerated.

Dapagliflozin and empagliflozin, as inhibitors of SGLT2, increase urinary glucose excretion, which is commonly believed to increase the risk of urinary tract infections. Urinary tract infections have been reported in dapagliflozin-treated patients in a slightly higher proportion than in placebo-treated patients in some global Phase III studies, although the rates of urinary tract infections (and serious urinary tract infections) observed in large clinical trials of dapagliflozin and other SGLT2i have been similar to placebo (16, 2). Increased urinary glucose excretion may also lead to an increased risk of developing genital infections. Genital infections are considered common side effects (in $\geq 1/100$ to $< 1/10$ patients), but the risk of these events is considered to be low due to the brief duration of treatment planned in this trial.

Dapagliflozin and empagliflozin modestly reduce blood pressure and may reduce blood volume from their diuretic effects, which could be a potential concern in patients with Covid-19. A pooled analysis of patients with T2DM and HF in the dapagliflozin development program, showed no increase of volume depletion events (17). In DARE-19 trial, there was no indication of increased risk for volume depletion and the number of acute kidney injury events was lower with dapagliflozin as compared with placebo.

Neither dapagliflozin nor empagliflozin have been shown to induce hypoglycemia in non-diabetic patients. In clinical pharmacology studies of dapagliflozin, healthy subjects have been treated with single oral doses of up to 500 mg and multiple oral doses of 100 mg up to 14 days without any hypoglycemic events. However, in patients with T2DM and on insulin or sulfonylurea medication, there is an increased risk of hypoglycemia. Patients with T2DM will be monitored in the hospital as part of standard of care, which includes blood glucose monitoring.

There have been reports of ketoacidosis, including DKA, in patients with T2DM taking dapagliflozin and other SGLT2 inhibitors. Diabetic ketoacidosis (which may occur without substantial elevation of blood glucose values – i.e. euglycemic diabetic ketoacidosis) is considered a rare (in $\geq 1/10000$ to $< 1/1000$ patients) adverse drug reaction for dapagliflozin in patients with T2DM (15). Patients treated with dapagliflozin who present with signs and symptoms consistent with ketoacidosis, including nausea, vomiting, abdominal pain, malaise, and shortness of breath, should be assessed

for ketoacidosis, even if blood glucose levels are below 14 mmol/L (250 mg/dL). If ketoacidosis is suspected, interruption of dapagliflozin (and other SGLT2 inhibitor) therapy should be considered, and the patient should be evaluated promptly. Predisposing factors to ketoacidosis include a low beta-cell function reserve resulting from pancreatic disorders (eg, type 1 diabetes, history of pancreatitis, or pancreatic surgery), insulin dose reduction, reduced caloric intake, or increased insulin requirements caused by infections, illness or surgery and alcohol use.

In DARE-19 trial, only two cases of DKA were reported in patients treated with dapagliflozin (versus 0 with placebo), both in patients with Type 2 diabetes; both were non-severe, and resolved quickly after discontinuation of study medication.

Appropriate measures are in place to monitor and minimize potential risks to participating patients, including the use of an DSMB that will continuously evaluate safety data. Patients with type 1 diabetes mellitus and patients with a history of DKA are excluded from this study. Monitoring of acid-base balance in patients with T2DM during hospitalization represents a standard of care in most institutions. Should there be an abnormal increase in anion gap and/or reduced bicarbonate levels, measurement of blood levels of ketones, lactate, and analysis of pH should be performed, and treatment with SGLT2 inhibitors should be temporarily discontinued, if DKA is suspected.

A diagnosis of DKA should only be made in a clinical setting consistent with DKA (based on patient history, symptoms, and physical exam) and in the absence of more likely alternative diagnoses and causes of acidosis (such as lactic acidosis). The following biochemical data should support diagnosis:

- Ketonemia ≥ 3.0 mmol/L and/or significant ketonuria (more than 2+ on standard urine sticks) in the absence of elevated lactate (lactate should be <2 mmol/L to be considered a potential DKA) and
- At least one of the following criteria suggesting high anion gap metabolic acidosis:
 - (a) Arterial or Venous pH ≤ 7.3
 - (b) Serum bicarbonate ≤ 18 mEq/L
 - (c) Anion gap $[\text{Na} - (\text{Cl} + \text{HCO}_3)] > 10$

If a diagnosis of DKA is confirmed, treatment with SGLT2 inhibitors should be permanently discontinued.

A10.8.2 Known Potential Benefits

Preliminary data from DARE-19 trial strongly suggest that use of SGLT2 inhibitors in patients hospitalized with Covid-19 may reduce the risk of organ failure or death from any cause via a number of pathophysiologic pathways, including favorable effects on endothelial function, oxidative stress, inflammation, oxygen-carrying capacity and tissue hypoxia, as well as through inhibition of glycolysis and lipogenesis.

This arm seeks to test the hypothesis that the SGLT2 inhibitors dapagliflozin or empagliflozin, on top of standard of care therapy, would decrease adverse events, including death and organ support free days. This trial will contribute to the body of generalizable knowledge about SGLT2 inhibitor therapy and the role of organ protection through SGLT2 inhibition in Covid-19 disease to minimize the risk of adverse events in patients hospitalized with Covid-19.

All patients in the study are expected to be treated optimally according to background local standard of care therapy, including treatments to control co-morbidities. SGLT2 inhibitors dapagliflozin or empagliflozin will be administered in addition to these treatments. These patients are hospitalized and will receive close medical attention, irrespective of treatment allocation.

A10.9 Event Adjudication

A subset of thrombotic events will be centrally adjudicated, with the proportion adjusted as needed based on agreement between the site and the event committee.

A10.10 Safety Analyses

The rate of SAEs (including DKA) will be monitored. The DSMB will review the number of events, the event rates, and the posterior mean and 95% credible intervals for the event rates, difference between arms, and odds-ratios between arms will be summarized.

A10.11 Statistical Analyses

